3.5 METABOLOMIC DATA ANALYSIS

To test the study hypothesis, a targeted metabolomics approach will be used to accurately measure the concentration of key metabolites in the TCA cycle and closely related pathways. The TCA cycle intermediates oxaloacetate, citrate, cisaconitate, isocitrate, α-ketoglutarate, succinate, fumarate and malate, alongside pyruvate and lactate will be measured using our rapid HILIC-Z Ion Mobility Mass Spectrometry (RHIMMS) method. We will also monitor the composition and concentration of accumulating ketones [such as acetoacetate, \(\beta \)-hydroxybutyrate [β HB], β -ketopentanoate and β -hydroxypentanoate]. The data will be processed for peak identification, and metabolite annotation using the Agilent MassHunter software suite. The Unified CCS Compendium PCDL and METLIN accurate mass libraries will be used for reliable identification of these metabolites. Investigations will study repeated measures in individual patients, compare serum, and MRI values [we note that Wright 2018 reported a robust correlation between serum and MRI defined brain levels of βHB] and study the relationship to clinical study outcomes. Samples will be blocked and randomised to minimise the impact of measurement error. Data analysis will include the evaluation of confounding variables to accurately link the outcome measures with metabolite measures and will be conducted by the specialist analysis team in the EdinOmics centre.

3.6 IMAGING DATA ANALYSIS

We will conduct structural magnetic resonance imaging (MRI) and physiological imaging including proton magnetic resonance spectroscopy (1H-MRS) to study the relationship between ketogenesis and both glycolytic / TCA metabolic pathways in the brain specified in the study hypothesis, and spectroscopic and structural markers of neuronal health. We will study whether baseline levels of key metabolic parameters are correlated with circulating metabolite measurements and selfreported and measured mental health assessments. Participants will be investigated at baseline and again between weeks 6-8 (last weeks of dietary intervention). For the primary imaging outcome, we will administer non-invasive proton (1H) magnetic resonance spectroscopy to assess for levels of a selection of glycolytic / TCA metabolites directly related to our study hypothesis relating to the mechanism of action of KD in BD [see supplementary submitted paper and Campbell 2019] e.g. lactate and those related to ketogenesis (e.g. β-hydroybutyrate). We will employ procedures based on those detailed in Wright 2018 which has provided proof of principle for measuring these parameters in their study. We will seek to identify the most promising glycolytic / TCA metabolite levels / ratios and longitudinal changes for use as a clinical response biomarker. We will also assess spectroscopic N-acetyl aspartate (NAA) in preselected brain regions and structural grey matter using voxel based morphometry as indicators of neuronal health. As part of secondary / exploratory analysis and hypothesis generation, we will acquire complementary physiological MRI capturing microstructural parameters, regional brain perfusion, and resting state functional MRI. These investigations will be conducted under the

supervision of an experienced neuroradiology academic and honorary NHS Consultant Neuroradiologist [name] and imaging data analysis will be conducted by the specialist imaging analysis team in Edinburgh Imaging. The Edinburgh Imaging Facility at the Royal Infirmary of Edinburgh / bioQuarter will be used which houses a state of the art 3 T neuro-optimised MRI scanner which is ideally suited to this study. The estimated scan time will be 45-60 minutes on each of the two occasions.

3.7 PROCESS EVALUATION

The process evaluation will explore the feasibility and acceptability of both the intervention, and elements of the study design, and it will be conducted following the Medical Research Council guidelines (Moore 2015). The process evaluation will assess: (i) intervention elements, i.e. acceptability, context, fidelity, exposure, and (ii) study related elements, i.e. acceptability of recruitment processes, outcome measures and contamination. It will also develop and refine the programme theory.

Quantitative process data will include adherence to the diet, measured via the finger prick blood tests to see if ketosis has been achieved. The dietitian will also complete weekly fidelity assessment of intervention delivery by the dietitians, using a fidelity checklist at the weekly update, which could be over the phone or via email. This will measure the extent to which the KD was delivered as intended.

Semi-structured telephone interviews will take place with 15 patients and 5 staff after the ten- week intervention period is complete and will take 40-60 minutes. Participants will be approached by telephone about taking part, and if they agree they will be sent an information sheet and consent form. At the interview the consent form will then be reviewed, and an audio recording of their consent to take part will be made and stored separately from the interview data. Patients will be purposively sampled to include a range gender, age, socioeconomic status and engagement with the intervention. Staff will be sampled to include dietitians from both centres and other health professionals including psychiatrists. Interviews will explore the acceptability of the evaluation methods and intervention; impact of the intervention; barriers and facilitators, contamination, suggestions for improvements as well as contextual factors influencing intervention impact. Interviews will be audio recorded on encrypted devices (to AES256 standard or above) and transcribed verbatim.

Qualitative data will be analysed using thematic analysis. Quantitative data will be analysed descriptively.

3.8 ECONOMIC EVALUATION

The economic evaluation will identify, measure and value the resource use and health related quality of life (HRQOL) impacts associated with the ketogenic diet in people with bipolar disorder. With input from PPI representatives a tailored health economics questionnaire for people with BD will be developed to measure typical service use patterns, employment, productivity, income levels, household food expenditure and health related quality of life using the EuroQol EQ-5D 5L instrument (www.euroqol.org) at baseline and all follow up. All staff time, equipment and consumable resources involved in delivering the intervention will also be identified and measured with input from the research team. For the intervention costs, all clinical (dietary and psychiatric) supervision (through checking adherence to prescribed diets, solving problems, and

identifying any adverse effects etc) will be measured and valued. The dietitian support over the 8-week dietary intervention period (plus 2-week cessation period) will be identified, measured, and valued.

In the future trial an NHS and personal social services (PSS) perspective will be adopted for the base case analysis as per NICE guidance however a sensitivity analysis will explore a full societal perspective so as to quantify the likely societal impacts of the intervention compared to TAU. Readily available unit costs such as NHS Reference costs (https://improvement.nhs.uk/resources/reference-costs/) and personal social services research unit (PSSRU) costs (Curtis 2019) will be attached to measured resource use. The within trial pilot analyses will be reported and presented as an exploratory incremental cost-utility ratio with the joint distribution of cost/utility pairs being represented on the cost-effectiveness plane and with a cost-effectiveness acceptability curve (CEAC) (Fenwick 2001) employing a range of UK willingness to pay thresholds.

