2.5 PRIMARY OUTCOME MEASURES

There is not a single primary outcome as this is a pilot study investigating the feasibility and acceptability of an intervention and gathering data on a range of other parameters as noted above. Therefore, all outcomes are equally important, and it will be essential for us to understand how to make all aspects of the study workable for a subsequent trial.

- Timeline estimates for future trial recruitment by measuring the number of interested participants and fully recruited participants from each avenue of recruitment during the estimated 4-month recruitment period
- Participant level of compliance with dietary interventions measured using fidelity checklists at weeks 0, 2, 4, 6, and 8, and daily ketone measurements during the 8-week intervention period
- Participant level of compliance with study assessments as recorded on the case report form at baseline and week 8
- Participant level of compliance with continuous study assessments measured using data from the study devices and apps (actigraph device, ketomojo device and app, and ilumivu app) or that sent directly to the research team by participants, during the 10-week study period
- Quality of life measured using the EQ5D-5L at baseline and week 8
 Productivity and activity impairment measured using the Work Productivity and Activity Impairment Questionnaire at baseline and week 8
- Participant resource use measured using a Within Trial Resource Use Questionnaire at baseline and week 8
- Staff time and cost in delivering dietary interventions, measured by keeping contemporaneous records throughout the 10-week study period
- Attrition rate measured using the number of participants who consent to participate who remain in the study until the end of follow-up at 10 weeks, to help inform estimation of sample size for a future trial
- Acceptability and experience of the study participants evaluated via telephone interviews after the main study has ended as part of a process evaluation

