3.3 KETOGENIC DIET INTERVENTION

All study participants will receive a low-carbohydrate, high-fat ketogenic diet intervention for an 8-week period, the first 2 weeks of which will be an adaptation period. The 8 weeks will then be followed by a 2-week cessation period. They will continue usual medical treatment from their regular care teams, including mental health services.

Based on the successful experience of the study dietitians in administering the KD to adults with epilepsy, we will identify a KD formulation associated with good levels of adherence. We will work closely with Patient and Public Involvement (PPI) representatives from Bipolar Scotland to develop and refine materials to support patients in adopting this diet.

Participants will have an initial meeting with a dietitian, lasting up to 2 hours, to discuss the details of the diet, food preferences, monitoring, and potential risks. They will request that participants complete a food diary to bring to their first appointment, to help plan what meals may be most appropriate for them to try on a KD. This will involve recording everything they eat and drink for 3 days prior to attending. International guidelines for the management of adults treated with ketogenic diet therapies (Mackenzie 2021) suggests that 'preparation and training must be individualised to provide the greatest likelihood of success', and we will endeavour to make this is a key part of our dietary initiation.

The diet will be gradually introduced over a 2-week period. Support will be via dietary supervision over the first few days to check adherence to prescribed diets, problem solve and identify any adverse effects, which will mainly occur over the phone or via email. Dietitians will provide guidance and practical support around establishing and characterising the diet, using recipe cards and planning, dietary booklets and providing advice on common problems. We will have support from a Professor of Behavioural Science to develop our approach to behavioural aspects of the intervention including barrier identification, problem solving, habit formation, social support, reducing negative emotions, and restructuring the environment.

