3.4.2 FOLLOW UP ASSESSMENTS

Participants will attend for repeat venepuncture and brain imaging in week 6, 7, or 8 of the 8-week intervention period. They will need to be fasted prior to this and will follow the same process as the baseline venepuncture and brain imaging. A psychiatrist will then repeat the baseline questionnaires and physical parameters as detailed above. The dietitian will clarify with them if they plan to continue the KD. If they do plan to continue the dietitian will provide further advice about how to do this. The dietitian will also be available for a further 4 weeks following the end of the 10-week study period, to provide ongoing advice and support if participants plan to continue the KD. We will aim for all follow up assessments to take place during one appointment.

Participants will be asked to monitor glucose and ketone measurements every day, wear their actigraph device, and record mood daily for the full 10-week study period. This will apply if they decide to stop the diet after 8 weeks or if they have decided to continue the diet. This will allow us to see if there are any changes in these parameters related to stopping the diet.

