4 STUDY POPULATION

4.1 NUMBER OF PARTICIPANTS

This study will aim to recruit 25 patients meeting the study criteria and consenting to take part.

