10 STATISTICS AND DATA ANALYSIS

10.1 SAMPLE SIZE CALCULATION

No formal sample size was calculated as this is a small feasibility study. We are not planning to draw firm conclusions about the efficacy of the diet.

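### The single-arm pilot promises an incremental cost-utility ratio, plane and CEAC without naming a comparator, so these cannot be read as cost-effectiveness against usual care

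*Protocol*

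**What the plan says.** On the economic output, Protocol section 3.8 says: "The within trial pilot analyses will be reported and presented as an exploratory incremental cost-utility ratio". The joint cost and utility pairs are to be "represented on the cost-effectiveness plane and with a cost-effectiveness acceptability curve (CEAC", over a range of UK willingness-to-pay thresholds.

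On the design, section 3.3 says: "All study participants will receive a low-carbohydrate, high-fat ketogenic diet intervention for an 8-week period". Participants keep their usual medical treatment alongside the diet. There is no control group. Section 4.1 sets the size: "This study will aim to recruit 25 patients meeting the study criteria and consenting to take part".

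The only comparator mentioned in section 3.8 is treatment as usual. It appears in the sentence on the future trial, where a societal sensitivity analysis is planned "so as to quantify the likely societal impacts of the intervention compared to TAU". No baseline, historical or modelled comparator is given for the pilot.

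On aims, section 2.3 frames the quality-of-life signal as a before-after assessment. Section 10.1 says "No formal sample size was calculated as this is a small feasibility study" and disclaims firm conclusions on efficacy. Section 10.2 commits to describing changes. Section 2.5 collects the EQ-5D-5L, WPAI and resource use at baseline and week 8.

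**The concern.** An incremental ratio, a plane of incremental pairs and a CEAC all describe a difference in cost and QALYs between two strategies. This study observes one. With no comparator named, an analyst following section 3.8 would have to choose one, and the natural choice from the pilot's own data is each participant's baseline. That choice attributes the whole change over 8 weeks to the diet.

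There are reasons to doubt that nothing would have changed otherwise, and they pull in opposite directions. Entrants must have had 3 months without a major mood episode (section 4.2), so some later worsening is plausible in any case. Recruitment relies largely on a call for volunteers (section 5.1), who then have weekly dietitian contact (section 3.3), so non-specific improvement is plausible too. Even the sign of the bias is unknown.

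At stake is the CEAC above all. It reports a probability that the diet is cost-effective, which is a comparative inference that this design cannot support.

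**Working it through.** The protocol states no ratio, cost, utility value or SD, so there is no figure of its own to reproduce. The argument rests on the passages set out above. The arithmetic below only shows how far the promised outputs depend on something the study does not observe.

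**Inputs from the protocol:** one arm; n = 25; utility measured at baseline and week 8, so the interval is 8/52 = 0.154 years.

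**Assumed inputs (none from the protocol):** observed mean utility gain 0.05; incremental cost £200 or £500 per participant, held fixed; linear change over the interval; unobserved utility change under usual care, d, from -0.05 to +0.06.

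**Formulae:** incremental QALY = (0.05 - d) × (8/52) / 2. Ratio = cost / incremental QALY.

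| d under usual care | Incremental QALY | Ratio at £200 | Ratio at £500 |
|---|---|---|---|
| -0.05 | 0.10 × 0.0769 = 0.00769 | £26,000 | £65,000 |
| 0 (baseline as comparator) | 0.05 × 0.0769 = 0.00385 | £52,000 | £130,000 |
| +0.02 | 0.03 × 0.0769 = 0.00231 | £86,667 | £216,667 |
| +0.05 | 0 | undefined | undefined |
| +0.06 | -0.01 × 0.0769 = -0.00077 | dominated | dominated |

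The observed data are identical in every row. Only d differs, and no measurement in the study informs it.

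**CEAC at one threshold.** Further assumptions: willingness to pay £20,000 per QALY, mean cost £100 with SD £60, SD of utility change 0.15, cost and utility uncorrelated, all 25 participants with data.

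- Standard error of mean net benefit = √[(20,000 × 0.15 × 0.0769)² + 60²] / √25 = √(230.8² + 60²) / 5 = 47.7.
- d = -0.05: mean net benefit 20,000 × 0.00769 - 100 = 53.8; z = 1.13; probability 0.87.
- d = 0: 76.9 - 100 = -23.1; z = -0.48; probability 0.31.
- d = +0.05: 0 - 100 = -100; z = -2.10; probability 0.02.

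The CEAC read at this threshold thus takes values from 0.02 to 0.87 for the same observations.

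**The case against.** Four points can be made for the plan.

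- **The output is labelled exploratory.** The ratio, plane and CEAC are not among the outcome measures in sections 2.5 and 2.6, and no sample size or decision depends on them. This stands, and it limits the severity.
- **A before-after increment can be computed.** A reader might infer that the result would have no meaning at all. The documents do not support that. EQ-5D-5L and resource use are collected at both times, and section 2.3 already frames quality of life as before-after. Such an increment can be read as a before-after change. What it cannot be is an estimate against usual care.
- **A separate health economics plan could name a comparator.** It could name baseline, or a historical or modelled comparator. It could not create a concurrent control, and section 3.8 already fixes the form of the output.
- **Rehearsing trial methods is a legitimate pilot aim.** Section 1.2 wants assessments carried out as they would be in a future trial. This stands, and it is why keeping the outputs with an explicit label is an acceptable alternative. An unstable ratio is likewise no argument against a plane or CEAC, which are the usual ways to show that instability.

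A reader might also infer that the intervention cost is understated, because "The dietitian will also be available for a further 4 weeks following the end of the 10-week study period". That does not follow. Section 2.5 defines the outcome as "Staff time and cost in delivering dietary interventions, measured by keeping contemporaneous records throughout the 10-week study period", and section 3.8 values support over the 8 weeks plus the 2-week cessation period. Sections 3.4.2 and 14.6 place the further support after the study period, for participants who plan to continue, with weekly contact only if both sides want it. The cost outcome is complete as defined.

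**Conclusion.** The point holds as a should-fix. Section 3.8 commits a single-arm pilot to three comparative economic outputs and names no comparator for them. From the pilot's own data the increment can only be before-after change, which rests on an untested assumption of no change without the diet. The outputs cannot be read as cost-effectiveness against usual care, and a reported probability of cost-effectiveness would go beyond the descriptive aims of sections 10.1 and 10.2.

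This conclusion rests on the text alone. The size cannot be established from the protocol: the spread from £65,000 per QALY to dominated (at £500), and from 0.02 to 0.87 on the CEAC, follows from assumed costs, utilities, SDs and threshold. It shows dependence on the missing counterfactual and predicts nothing about this study's results. The planned data collection and the costing window are unaffected.

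**What to change.** In section 3.8, reserve the incremental cost-utility ratio, the plane and the CEAC for the future randomised trial. For the pilot, report mean intervention cost per participant with a confidence interval, and resource use, EQ-5D-5L and WPAI at baseline and week 8 with confidence intervals and completeness.

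If the outputs are kept to rehearse the methods, section 3.8 should:

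- name the participant's own baseline as the comparator;
- state the assumption of no change without the diet;
- state that the result is not an estimate against treatment as usual;
- state that no probability of cost-effectiveness will be concluded from it.

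Either route is a change of wording only, since all the data needed are already collected. The downside is a less prominent economic output from the pilot.

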3.9 PATIENT AND PUBLIC INVOLVEMENT

Public involvement has informed our planning and research design from the earliest stages through consulting with online and offline BD networks. We participated in several large public online BD forums and performed a text mining study to gather all posts mentioning experiences on a KD. We performed a formal text mining analysis of 274 individual reports [Campbell BJP Open 2019]. The many common experiences with KD in the BD population have informed our research design.

[name] from Bipolar Scotland (national charity for people who live with bipolar disorder) has provided key insights to inform our recruitment strategy and planning of proposed interaction with patient and public groups. Bipolar Scotland were consulted on strategies for raising awareness of the study, recruitment and intervention adherence and contributed an article summarising KD research for their newsletter ahead of a visit to give a talk and host a question-and-answer session. [name] will remain on the project team throughout the pilot study, which will have patient and public involvement at its centre, as ensuring all aspects of the study are acceptable to participants is vital.

We have given 4 talks to BD local support groups on the ketogenic diet including question and answer sessions. Recently we presented a talk on ketogenic diet at the Bipolar Scotland annual conference. [name] has been in regular communication with members to discuss what they would like to see in a trial of KD.

[name], their Mental Health Food and Nutrition representative, has also agreed to give advice and support. We will form a study PPI group including representation from Bipolar Scotland and The Scottish Association for Mental Health (SAMH) groups and have identified a PPI Lead who will be funded 0.2 WTE throughout the project to lead PPI activities and regular meetings and to develop a 10 episode online video series with content (e.g. detailing experiences on a KD) to be defined following PPI consultations. Our PPI group will advise on all aspects of the study including the intervention, recruitment, retention, outcomes measures and dissemination.

